2.2 Secondary Objectives

1. Determine six-month and twelve-month survival (**overall mortality endpoint**) after treatment with ENCORE.
2. Determine **late toxicity endpoint** (>90 days to 12 months), as tracked prospectively after treatment using CTCAE v4.0 criteria.
3. Determine patient-reported health related **quality of life endpoint** (HRQOL) as measured by changes between pre-treatment and 6-week, 6-month, and 12-month post treatment scores on the standardized SF-36 questionnaire.

4. Evaluate **stricter efficacy endpoint** of ENCORE treatment, as defined by number of patients who have had 50% reduction in any VT therapies (ATP or ICD shocks) after ENCORE treatment (6 months before vs. 6 months after treatment, with a 6 week blanking period immediately after treatment). For patients with PVC-induced cardiomyopathy, the stricter efficacy will be >50% reduction in PVC burden based on ambulatory heart monitors.
5. Evaluate **strictest efficacy endpoint** of ENCORE treatment, as defined by number of patients who have had 95% reduction in any VT (ATP or ICD shocks) after ENCORE treatment (6 months before vs. 6 months after treatment, with a 6 week blanking period immediately after treatment). For patients with PVC-induced cardiomyopathy, the strictest efficacy will be abolition of PVC burden (<1%) based on ambulatory heart monitors.
6. Evaluate the **most clinically useful efficacy endpoint** of ENCORE treatment, namely, number of patients with reduction specifically in ICD shocks (6 months before vs. 6 months after treatment, with a 6 week blanking period immediately after treatment). For patients with PVC-induced cardiomyopathy, the most clinically useful efficacy will be improvement in cardiac function in the setting of any improvement in PVC burden.
7. Evaluate **longer-term durability endpoint** of ENCORE treatment, as defined by number of patients with reduction in VT therapies (ATP or ICD shock and ICD shock alone) during the early phase (treatment to 6 months, with 6 week blanking period) vs. the late phase (6 months to 1 year). For patients with PVC-induced cardiomyopathy, the longer-term durability efficacy will be persistence of any reduction in PVC burden based on ambulatory heart monitors during early phase vs. late phase.

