3.0 PATIENT SELECTION

3.1 Inclusion Criteria

1. DOCUMENTED VT:
 - a. Patient must have documented sustained monomorphic ventricular tachycardia as documented on either a 12-lead ECG or intracardiac ICD interrogation
 - OR—
 - b. Monomorphic PVCs documented on a 12-lead ECG.
2. ANTIARRHYTHMIC MEDICATION: Patient must have failed or become intolerant to at least one antiarrhythmic medication (amiodarone, sotalol, or mexiletine).
—AND—
3. CATHETER ABLATION: Patient must have failed at least one invasive catheter ablation procedure, or have a contraindication to a catheter ablation procedure (e.g., LV thrombus, severe pulmonary disease), or have VT thought to arise from a protected location (e.g., epicardial VT with history of previous cardiac surgery).
4. MINIMUM VT BURDEN: Patient must have either:
 - a. At least 3 VT episodes (sustained VT, ICD ATP or ICD shock) over previous 6 months prior to enrollment
 - OR—
 - b. >20% PVC burden with a cardiomyopathy (LVEF<50%)
5. Patient must be deemed medically fit for stereotactic body radiation therapy by the treating physician.
6. Patient must be \geq 18 years old.
7. Patient must be able to understand and be willing to sign an IRB approved written informed consent document.

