11.2 Sample Size Justification

A total of 19 patients will be enrolled, which provides an optimal balance between assuring a high likelihood of safety (Phase I) with a preliminary assessment of efficacy (Phase II).

For the phase I component, the baseline rate of SAEs for catheter ablation is assumed to be 10-15%. Given the population being studied and a reasonable expectation that patients may be at a higher than typical risk of toxicity from any salvage therapy, we assume that SAE rates up to 20% would be clinically acceptable. Having said that, given that this is a totally noninvasive technique, it may well be that rates of toxicity are lower than that expected with catheter ablation. After exploring patient ranges from 15-25 patients, it was determined that 19 patients would provide a 75.4% power to detect an SAE rate about 20% (range, 5%-20%, $\alpha = 0.0829$).

For the phase II component, while some single institution series report much higher success rates, the baseline efficacy rate of catheter ablation in prospective trials ranges from 50-65%. As this is a salvage therapy in a high risk population, we assume that efficacy rates as low as 40% would be clinically acceptable. Using the 19 patient sample determined above, it was determined that 19 patients would provide 81.5% power to determine that ENCORE is not worse than 40% effective for the treatment of VT (range, 40-65%, $\alpha = 0.0885$).

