11.3 Analytic Plan for Primary Objectives

SAEs defined by CTCAE v4.0 criteria within 90 days of ENCORE that are possibly/probably/definitely related to study treatment will be recorded. ENCORE therapy will be deemed safe if the rate of SAEs is $\leq 20\%$. An additional early stopping rule dictates that if 5 or more out of the first 10 patients develop ENCORE related SAEs, the trial will be halted.

The number of ICD therapies delivered in the 6 month periods preceding and following ENCORE therapy will be recorded for each patient by interrogation of the ICD. ENCORE therapy will be deemed efficacious if there is a reduction in ICD therapies before and after treatment. The proportion of patients with efficacious ENCORE therapy will be calculated, with the intent of demonstrating at least 40% efficacy.

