11.4 Analytic Plan for Secondary and Exploratory Objectives

Adverse events will be tabulated by type and grade.

Descriptive statistics will be used to describe efficacy and strict efficacy, changes in SF-36 scores, changes in ECGI, differences in purely ECGI derived vs. clinically-derived target volumes.

Dose-volume parameters to the ENCORE target as defined by ECGI and the clinical target volume will be correlated with the reduction in VT through descriptive statistics and Cox regression.

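### For ICD patients the durability endpoint compares about 4.6 countable months with 6, without a rate, and does not state what a reduction is measured against

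*Combined protocol and SAP*

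**What the plan says.** Section 2.2, item 7, defines longer-term durability "as defined by number of patients with reduction in VT therapies (ATP or ICD shock and ICD shock alone) during the early phase", with the phases given as "treatment to 6 months, with 6 week blanking period) vs. the late phase (6 months to 1 year". For patients with PVC-induced cardiomyopathy the same item asks for "persistence of any reduction in PVC burden based on ambulatory heart monitors during early phase vs. late phase".

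Items 4 to 6 of that list compare "6 months before vs. 6 months after treatment, with a 6 week blanking period immediately after treatment": the period named first is the reference and the second is the comparison.

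The unit is a count. Section 11.3, on the primary endpoint, states: "The number of ICD therapies delivered in the 6 month periods preceding and following ENCORE therapy will be recorded for each patient". No section scales counts to observed time. Section 11.4 says "Descriptive statistics will be used to describe efficacy and strict efficacy, changes in SF-36 scores, changes in ECGI". It does not name durability, and it gives no rule for scaling or for zero counts.

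**The concern.** The early phase ends and the late phase begins at 6 months, so blanking removes six weeks from the early phase only. Comparing raw counts across windows of different length makes an unchanged rate look like a rise.

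The wording also leaves open what a reduction is relative to. It may mean fewer therapies late than early, or fewer than before treatment in each phase. A patient with no therapies after blanking cannot be a success on the first meaning and is one on the second.

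This is the only named endpoint on whether the antiarrhythmic effect lasts beyond 6 months. With 19 patients, a few classifications one way or the other would change what is reported.

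**Working it through.** **1. The plan's own figures.** None is given for durability. The primary design figures in section 11.2 reproduce with exact one-sided binomial rules. The cut-offs are inferred, because the plan does not state them.
- Efficacy, at least 11 of 19: P = 0.0885 at 40% and 0.8145 at 65% (plan: alpha 0.0885, power 81.5%).
- Safety, at most 1 of 19: P = 0.0829 at 20% and 0.7547 at 5% (plan: alpha 0.0829, power 75.4%).

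Neither depends on the durability endpoint.

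**2. Window lengths (section 2.2, item 7).** Six months is 182.6 days. Early: 182.6 − 42 = 140.6 days, or 140.6/30.44 = 4.62 months. Late: 182.6 days. Ratio: 182.6/140.6 = 1.30 (6/4.5 = 1.33 if the early phase is rounded to 4.5 months).

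**3. Reduction read as early to late.** Assume a constant post-treatment rate λ per month, that is, a fully maintained effect. The documents give no such rate, so a range is shown. Early count E has mean 4.62λ, late count L has mean 6λ, and the two are independent. P(L > E) = Σ P(E = x) P(L > x), and similarly for L < E.

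| λ per month | Poisson: late below / tie / late above | Negative binomial, k = 0.5: late below / late above | Poisson, two 6-month windows: late below = late above |
|---|---|---|---|
| 0.25 | 29.2 / 25.6 / 45.2% | 30 / 37% | 38% |
| 0.5 | 30.0 / 17.1 / 53.0% | 36 / 43% | 42% |
| 1 | 28.1 / 11.4 / 60.6% | 40 / 47% | 44% |
| 2 | 23.9 / 7.3 / 68.8% | 42 / 50% | 46% |

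With 4.5 months, the Poisson figures are 45.8, 54.0, 62.0 and 70.7% for late above early, and 28.5, 28.9, 26.7 and 22.2% for late below. The last column isolates the effect of the windows: with equal exposure the two directions balance. At a low rate, 0.5 per 6 months, a tie is the likeliest result (21.2 / 49.6 / 29.2%).

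**4. Reduction read as against pre-treatment in each phase.** Take a 6-month baseline count of 6 (an assumption; eligibility under section 3.1 is "At least 3 VT episodes (sustained VT, ICD ATP or ICD shock) over previous 6 months prior to enrollment"). With a true reduction r, the late mean is 6(1 − r) and the early mean is that divided by 1.30. A reduction shows if the count is 5 or fewer (Poisson).
- r = 50%: means 2.31 and 3.00; 96.9% early, 91.6% late.
- r = 25%: means 3.47 and 4.50; 86.2% early, 70.3% late.
- r = 0: means 4.62 and 6.00; 68.2% early, 44.6% late.

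The bias has the same direction on this reading.

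**5. Zero counts.** On the early-to-late reading, E = 0 gives P(L < E) = 0 whatever the rate. On the pre-treatment reading, a patient with no therapies after blanking is below any non-zero baseline in both phases and counts in both.

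**6. Check of the remedy.** With rates, the baseline is 6/6 = 1 per month. The early count must then be 4 or fewer (4/4.62 = 0.87; 5/4.62 = 1.08), and the late count 5 or fewer.
- r = 50%: 91.5% early, 91.6% late.
- r = 25%: 73.2% early, 70.3% late.

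The gaps of 5.3 and 15.9 points shrink to about 0 and 3. What remains comes from whole-number counts.

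**The case against.** The best defence is that item 7 already means reduction against pre-treatment, assessed once in each phase. The PVC sentence speaks of a reduction that persists and uses the same early-versus-late phrase. On that reading complete responders count, and much of the remedy is what the authors intended. This stands as a plausible reading. A reader might infer from the ICD sentence alone that complete responders can never count, or that the endpoint ranks patients in reverse. The documents do not support that as an unconditional statement: it follows from the early-to-late reading, which the pattern of items 4 to 6 favours and the PVC sentence does not.

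The sizes are also conditional. The rates are assumed, and overdispersion shrinks the asymmetry, though its direction stays. Part of the low share with a late reduction would occur with equal windows too (38-46%, against 24-30% here, Poisson). A patient with zero in both phases is a tie, not a loss.

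Finally, the endpoint is the seventh secondary objective of a small single-arm study. It is descriptive, and no test, threshold or decision depends on it. None of this removes the unequal windows, which bias the comparison on both readings.

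**Conclusion.** The point holds for ICD patients. Raw counts over about 4.6 and 6 months are compared without a rate, so a constant rate yields about 30% more late therapies and a maintained effect leans toward apparent loss.

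If reduction means early to late, late exceeds early in about 45-71% of patients and falls below it in 22-30% under Poisson counts; with k = 0.5 the figures are 37-50% and 30-42%. These assume constant rates of 0.25 to 2 per month and independent counts, and the Poisson ranges span early phases of 4.5 and 4.62 months. If reduction means against a baseline of 6, the early-to-late drop for a maintained effect is 5.3 points at a 50% reduction and 15.9 points at 25%.

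The reference period is unstated, and the two readings class a patient with no early therapies in opposite ways. That is an ambiguity to settle, not proof that the best responders are excluded. PVC burden is a percentage, so window length does not bias it. Nor does the point reach the primary analysis: the section 11.2 figures reproduce and are unaffected.

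**What to change.** In section 2.2, item 7, and section 11.4, define an ICD patient as durable if the number of therapies per month of observed follow-up is below the pre-treatment monthly rate in both the early phase (after blanking) and the late phase. A zero count in a phase is then a maintained reduction. Report the late-to-baseline rate ratio as well. Do both for ATP or shock, and separately for shock alone.

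State the denominator. Eligibility can be met by sustained VT or ATP, so a patient may have no baseline shocks and cannot show a reduction in them. List such patients, and any with no observed late phase, separately.

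PVC patients need no window correction, since their endpoint is already framed as persistence of a reduction in a percentage.

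The cost is wording in two sections. Device interrogations are already scheduled through 12 months (section 7.0), and the sample size does not change.

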2.3 Exploratory Objectives

1. To better understand the **mechanisms and timing of radiotherapy injury**, we will obtain serum blood markers of myocardial injury (troponin), endothelial injury (E-selectin), fibrosis (galectin-3) and prothrombotic markers (von Willibrand factor) at baseline, 3 days and 3 months after ENCORE treatment.
2. Evolution of **electrical remodeling** as obtained with noninvasive ECGI from baseline to 3 months and 12 months after ENCORE treatment
3. To better understand the effect of radiotherapy on **edema, fibrosis, cardiac inflammation, cardiac metabolism and localized cardiac function**, we plan to use serial cardiac imaging (DE-cMRI when possible, FDG-PET in all) at baseline, 3 days and 3 months after ENCORE treatment

3.0 PATIENT SELECTION

3.1 Inclusion Criteria

1. DOCUMENTED VT:
 - a. Patient must have documented sustained monomorphic ventricular tachycardia as documented on either a 12-lead ECG or intracardiac ICD interrogation
 - OR—
 - b. Monomorphic PVCs documented on a 12-lead ECG.
2. ANTIARRHYTHMIC MEDICATION: Patient must have failed or become intolerant to at least one antiarrhythmic medication (amiodarone, sotalol, or mexiletine).
—AND—
3. CATHETER ABLATION: Patient must have failed at least one invasive catheter ablation procedure, or have a contraindication to a catheter ablation procedure (e.g., LV thrombus, severe pulmonary disease), or have VT thought to arise from a protected location (e.g., epicardial VT with history of previous cardiac surgery).
4. MINIMUM VT BURDEN: Patient must have either:
 - a. At least 3 VT episodes (sustained VT, ICD ATP or ICD shock) over previous 6 months prior to enrollment
 - OR—
 - b. >20% PVC burden with a cardiomyopathy (LVEF<50%)
5. Patient must be deemed medically fit for stereotactic body radiation therapy by the treating physician.
6. Patient must be \geq 18 years old.
7. Patient must be able to understand and be willing to sign an IRB approved written informed consent document.

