2.0 OBJECTIVES

2.1 Primary Objectives

1. Phase I - Demonstrate acute (≤ 90 days) safety of noninvasive stereotactic cardiac ablation radiotherapy (ENCORE). The **primary safety endpoint** is defined by a $\leq 20\%$ rate of serious adverse events (SAEs) using CTCAE v4.0 criteria that are possibly/probably/definitely related to study treatment, based on previously published data for expected invasive catheter-based VT-ablation procedures.
2. Phase II - Demonstrate preliminary efficacy of ENCORE. The **primary efficacy endpoint** is defined by the number of subjects with a reduction in ICD therapies (ATP and ICD shocks) comparing the period six months before ENCORE treatment to the six months after ENCORE treatment as adjudicated by continuous ICD monitoring. There will be a six-week “blanking period” after therapy to allow for ablation effect. For patients with PVC-induced cardiomyopathy, the primary efficacy will be any reduction in PVC burden based on ambulatory heart monitors.

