We anticipate that most or all of the patients who are enrolled into this study will have cardiac defibrillators (ICDs) to treat ventricular arrhythmias. Historically, the presence of an ICD has been a contraindication to performing MRI for various theoretical and observed concerns. Over the course of the past decade, great strides have been made to safely allow patients with ICDs to undergo MRI scans. These are reviewed in several recent publications (42-53). The most prominent of these is the completion of a large registry to characterize the risks of undergoing MRI with a cardiac device (MAGNASAFE.org). This registry and other publications (50) have defined the substantial safety margin of MRI use in patients with cardiac devices, and these studies form the basis for an upcoming professional guideline statement regarding the expanded and safe use of MRI in patients with cardiac devices (anticipated 2016 release). In short, the MAGNASAFE registry was a multicenter trial of 1,500 patients with cardiac devices who underwent MRI scanning on a 1.5 T scanner. Of the 1500 MRI scans, only 1 patient developed a clinical event (generator failure due to inappropriate sensing) which was deemed to be caused by inappropriate ICD programming. The overall positive results of the MAGNASAFE study have resulted in the national CMS National Coverage Determination (NCD) allowing for coverage of MRIs in patients with cardiac devices if they are performed in a research study that meets CED (coverage with evidence development) criteria.” (Medicare website: CAG-00399R2). Since the release of MAGNASAFE, a number of trials including patients who are specific to our population (patients with VT, with implanted ICD, undergoing cardiac MRI) have been published (42-53). In these studies, there were no adverse effects of cardiac MRI with appropriate pre-scan ICD programming, further supporting the overall safety of this scan in the appropriately selected patients.

A second major advance is the development of MRI-conditional cardiac devices, which are now commercially available from several manufacturers (Medtronic, Biotronik). Whenever possible, we plan to use these devices for new implants at our hospital. However, we expect most patients who enroll into this study will have older legacy devices, which do not have specific MRI-conditional labeling.

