In this study, we recognize the potential risks involved with MRI in patients with ICDs, and these risks will be shared with patients in full disclosure, using language

and images from a recently published “Cardiology Patient Page” article (54). MRI remains the gold standard for assessment of fibrosis and edema, and we believe the large benefits of precision guidance of radiotherapy outweigh the small potential risks of ICD system changes. Patients who are unwilling to accept these risks, or patients in whom we believe the risks to be excessive will not undergo MRI. We will then use clinically available imaging, such as nuclear MPI/SPECT, which is less specific and sensitive than MRI.

Patients in whom we will NOT offer an MRI include:

- a) Newly implanted ICD system (any component added < 6 weeks)
- b) Dependence on ICD system for pacing (complete heart block or severe sinus node dysfunction without ventricular escape)
- c) Presence of abandoned, fractured or epicardial cardiac leads
- d) Active noncardiac implanted device (other than cardiac device)
- e) Abdominal position of cardiac device
- f) Battery voltage of ICD at elective replacement interval
- g) Increased risk to administration of IV gadolinium such as renal impairment (estimated glomerular filtration rate (eGFR) < 40) or previous adverse reaction to IV gadolinium.
- h) Patient preference

For patients who undergo MRI, several safeguards have been developed as “best practices” and will be used for this study. These include:

- a) Supervision of appropriately trained personnel for the duration of the MRI scan
- b) Pre-treatment and post-treatment ICD device checks
- c) Pre-treatment ICD programming per standardized protocol (MAGNASAFE registry) to minimize chances of untoward ICD effects, including asynchronous or inhibited pacing mode (VOO/DOO or VVI/DDI setting), disabling magnet response, disabling episode memory, and disabling therapies for tachyarrhythmia. A full risk-mitigation protocol has been developed and is available as a supplement to this protocol.

[figure not shown]

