7.0 STUDY CALENDAR

	Screening	Baseline	ENCORE tx	Day 3	2 wk	4 wk	6 wk	3 mo	6 mo	12 mo	Extended F/U**
Informed consent	X										
Medical history	X										X
Pregnancy test	X										
Device interrogation (Standard of care)	X		X	X	X	X	X	X	X	X	X
24 Hour heart monitor* (Standard of care)	X						X	X	X	X	
SF-36 QoL		X					X		X	X	
12-lead EKG		X		X			X	X	X	X	
NIPS		X									
Cardiac CT + ECGI		X						X		X	
Cardiac MRI + PET		X		X				X			
Adverse events assessment		X	X	X	X	X	X	X	X	X	X
Blood work		X		X			X	X			

* For patients with PVC-induced cardiomyopathy-indications only

** Patients will be followed as per routine clinical practice, with data being collected from the medical record on outcomes for up to 5 years post-completion of study treatment. Device interrogation, 24 hour heart monitors, and imaging will be performed as clinically indicated but are not mandated by the protocol. Capture of AEs will be performed as described in Section 5.1.

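### On the VT route nothing secures six months of ICD recording before treatment, yet the primary efficacy endpoint compares raw ICD-therapy counts over that window

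*Combined protocol and SAP*

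**What the plan says.** **Eligibility.** Section 3.1 item 1a reads "Patient must have documented sustained monomorphic ventricular tachycardia as documented on either a 12-lead ECG or intracardiac ICD interrogation". The ECG alone is enough. The burden rule for this route, item 4a, reads "At least 3 VT episodes (sustained VT, ICD ATP or ICD shock) over previous 6 months prior to enrollment", so three sustained episodes qualify without any device therapy. Neither 3.1 nor the exclusions in 3.2 mention having an ICD or how long it must have been in place.

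**Endpoint.** Section 2.1 defines primary efficacy by a fall in ATP and shocks, "comparing the period six months before ENCORE treatment to the six months after ENCORE treatment as adjudicated by continuous ICD monitoring". Section 11.3 repeats it: "The number of ICD therapies delivered in the 6 month periods preceding and following ENCORE therapy will be recorded for each patient by interrogation". The only primary endpoint that needs no ICD is PVC burden, which is reserved for PVC-induced cardiomyopathy. The 24-hour monitor in section 7.0 carries the matching footnote, "For patients with PVC-induced cardiomyopathy-indications only".

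**Evaluability.** Section 4.5 makes anyone who receives the full single-fraction dose evaluable for primary and secondary objectives. It sets no condition on device data.

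**What is expected about devices.** Section 4.1.1 says "We anticipate that most or all of the patients who are enrolled into this study will have cardiac defibrillators (ICDs) to treat ventricular arrhythmias". It also expects most of these devices to be older legacy models. Its list of patients who will not be offered MRI begins with "Newly implanted ICD system (any component added < 6 weeks", which bars the scan and not enrolment. Section 4.2 plans a baseline NIPS through the ICD lead, and section 7.0 schedules device interrogation at screening.

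**The concern.** The endpoint takes for granted a device that was recording throughout the six months before treatment. The eligibility criteria do not ensure this, and no section says what to do when the record is short or absent.

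Suppose a VT patient's first ICD was implanted one to three months before treatment. The before count then covers one to three months and the after count up to six. On raw counts the patient can be scored as a failure despite a real fall in the therapy rate. This differs from a patient who was monitored throughout and simply had no therapy: here the device was not there to count.

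Without a rule, such a patient could be scored as a failure, dropped or rate-adjusted, and the choice could be made after the data are seen. Each choice moves the proportion that is set against 40% in a single-arm trial of 19.

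**Working it through.** **1. The plan's own figure.** Section 11.2 gives n = 19, 40% against 65%, alpha 0.0885 and power 81.5%. With X ~ Binomial(19, p) and success declared at X ≥ 11:
- alpha = P(X ≥ 11 | 0.40) = 0.0885
- power = P(X ≥ 11 | 0.65) = 0.8145

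Both reproduce. Neighbouring cut-offs do not: 10 gives 0.186 and 0.913, and 12 gives 0.035 and 0.666. The cut-off of 11 is inferred from this match; the plan does not print it. The calculation uses all 19 patients, with no allowance for a missing outcome.

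**2. Cost of a patient with no usable outcome.** The number of such patients is not given. Each is 1/19 = 5.3 percentage points. If k patients count as failures and the cut-off stays at 11, power = P(Binomial(19 − k, 0.65) ≥ 11):
- k = 1: 72.8%
- k = 2: 61.9%

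Dropping them and resetting the cut-off to keep alpha at or below 0.0885 still requires 11 successes of 18 or of 17, so power is the same.

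**3. Truncated baseline (illustration).** Assume Poisson counts, 6 therapies per six months before treatment, and a true halving. With m months of device time before treatment:
- before count B ~ Poisson(6 × m/6) = Poisson(m)
- after count A ~ Poisson(3) over six months; or, if the six-week blanking leaves 6 − 1.5 = 4.5 months, A ~ Poisson(3 × 4.5/6) = Poisson(2.25)
- P(reduction scored) = Σ P(B = b) × P(A ≤ b − 1)

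| Months of device data before | No blanking (6 months after) | Six weeks blanked (4.5 months after) |
|---|---|---|
| 6 | 80.0% | 87.6% |
| 3 | 41.7% | 54.0% |
| 2 | 24.7% | 35.4% |
| 1 | 9.4% | 15.5% |

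Other assumed rates show the same pattern. With six weeks blanked and 6, 3 and 1 months of baseline, 3 therapies per six months gives 75%, 46% and 16%; 12 per six months gives 96%, 62% and 11%.

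**4. Effect of item 4a.** If the three qualifying episodes were all device-recorded therapies within the short record, then B ≥ 3. With one month of data, B is Poisson(1) conditioned on B ≥ 3. Values of B of 3, 4, 5 and 6 then have probability 0.764, 0.191, 0.038 and 0.006. With A ~ Poisson(3), the chance of a reduction is 0.764 × 0.423 + 0.191 × 0.647 + 0.038 × 0.815 + 0.006 × 0.916 + a remainder of about 0.001 ≈ 48%. With six weeks blanked it is about 66%. The fall is then real but much smaller.

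**5. Comparing rates instead.** Score a reduction when A/6 < B/m. Without blanking, the chance at three months rises from 42% to 73%, and at one month from 9% to 60%, against 80% with a full baseline. The remaining gap is mostly patients with no therapy in the short record: at one month P(B = 0) = e^(−1) = 37%, so no rate rule can exceed 63%.

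**The case against.** The strongest reply is that the problem will seldom arise.

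- **No ICD at all.** Baseline NIPS is delivered through the ICD lead and interrogation is scheduled from screening onwards, so a VT patient without a device could not complete the work-up as written. This stands, and it makes that case unlikely. It does not close it: neither procedure is an eligibility criterion, and the NIPS contraindications in section 4.2 are not trial exclusions.
- **Recent first ICD.** Section 4.1.1 expects mostly older legacy devices, and the drug and ablation criteria in 3.1 suggest long-standing disease. A reader might infer from the MRI list that the sponsor foresees first implants within six weeks of enrolment. The documents do not support that: the item covers any added component, including a lead or generator change in an old system. What stands is narrower. NIPS shows that a device is present at baseline, not that it recorded for the previous six months, and nothing else secures that.
- **Size.** The illustration depends on assumed rates, on how blanking is counted and on whether the 4a episodes were device therapies. This too stands, which is why ranges are given. The direction does not change.
- **Remedy.** A blanket six-month device requirement would defer refractory patients from a trial whose phase I safety endpoint needs no ICD history. That is a fair objection, and the fix below does not rely on such a requirement.

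**Conclusion.** The gap is certain on the text; its frequency is unknown. Eligibility and evaluability admit VT patients whose before count is truncated, and the raw-count rule then biases against treatment. One patient scored as a failure for this reason costs 5.3 points and takes power from 81.5% to 72.8%; two take it to 61.9%. Under the stated Poisson assumptions, the chance of scoring a true halving falls from 80-88% to 42-54% with three months of baseline and to about 9-16% with one. It falls less if the qualifying episodes were all device-recorded therapies.

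Two stronger readings are tempting and should not be drawn. One is that the trial will enrol a material number of VT patients with no ICD; the planned NIPS and interrogation point the other way. The other is that the sample-size calculation is wrong; it reproduces exactly. The point deserves correction because with 19 patients one or two cases matter and the cost is low.

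**What to change.** 1. **Section 3.1 item 4a, VT route only:** require an ICD with retrievable therapy data before treatment. The PVC route (4b) stays exempt.
2. **Sections 2.1 and 11.3:** where the device record covers less than the full window, define a reduction as fewer ICD therapies per month of device-monitored time after treatment than before. When both windows are a full six months, this is the same as comparing counts.
3. **Section 4.5:** state that a VT patient with no pre-treatment device record stays evaluable for safety, and fix in advance how that patient enters the efficacy analysis, for example as a non-responder in the comparison with 40%.

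**Cost.** A few sentences and no added procedure. A VT patient without an ICD would not be enrolled, which the planned NIPS already largely implies. Rates from short baselines are noisier, and a short record with no therapies still cannot show a reduction. Requiring a full six months of ICD data is a stricter option that would remove the truncation, at the price of deferring some patients.
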